2. STUDY OBJECTIVE

2.1. Primary Objective

The primary objective is to evaluate the efficacy of the combination of rituximab and ibrutinib versus the historical experience with rituximab alone in the upfront treatment of cGVHD. The primary efficacy endpoint is to estimate the proportion of patients that are alive and off IST at 12 months following initiation of treatment. To meet this endpoint, patients need to remain off IST (e.g. sirolimus, tacrolimus, steroids, etc). for at least 8 weeks. The use of rituximab and ibrutinib are not considered IST for this endpoint.

2.2. Secondary Objective(s)

Efficacy

To estimate:

- Chronic GVHD response (CR + PR, both individual organ response and overall response, according to 2014 NIH Response Criteria Working Group Report) – See Appendix G.
- Cumulative steroid exposure (total mg methylprednisolone or equivalent).
- Time to discontinuation of systemic immunosuppression (defined as the date that all systemic IST has been discontinued after resolution of all reversible manifestations of cGVHD. Discontinuation of immunosuppressive medications for the purpose of inducing an anti-tumor response after the development of recurrent or secondary malignancy will not be counted as successful discontinuation of IST).
- Failure-free survival (defined as being alive without the requirement for second-line cGVHD therapy). See section 6.3 for definition of second-line cGVHD therapy.
- Non-relapse and overall mortality

Safety

To estimate:

- Incidence of grade ≥ 3 adverse events, possibly or probably related to either ibrutinib and/or rituximab.

- To evaluate the safety and tolerability of combination of rituximab and ibrutinib versus the historical experience with rituximab alone in the upfront treatment of cGVHD.

2.3. Exploratory Objective

- To evaluate laboratory-based correlates associated with response to treatment.

3. STUDY DESIGN

3.1. Overview of Study Design

The rationale for the study concept is provided in [Section 1.3](#).

This is a phase II trial evaluating the safety and efficacy of the combination of Ibrutinib and Rituximab as primary treatment of cGVHD. We plan to enroll 35 patients on this study. Patients will be formally monitored monthly for 12 months to evaluate for outcome and safety endpoints. All other assessments will be done at the physician's discretion or institutional standards. All patients, responders and treatment failures, will be followed for a period of one year from the time of initiation of therapy. The primary endpoint will be the proportion of patients that are alive and off all systemic IST at 12 months following initiation of treatment.

Eligible patients will be those with a first episode of symptomatic cGVHD, requiring systemic immunosuppression for control of symptoms. Following study entry, patients will be started on:

[figure not shown]
1. Ibrutinib 420mg PO QDAY (28-day cycles) for a total of 12 cycles unless discontinued early due to toxicity (see stopping rules in section 5.1.1.4). Dose adjustments are required for patients with hepatic impairment or those receiving concomitant voriconazole or posaconazole or other strong CyP 3A4 inhibitor according to sections 5.1.1.5 and 5.1.1.6.
2. Rituximab 375mg/m² IV weekly x 4 weeks (to be started on study day 7 ± 3 days), then 375mg/m² IV q3months x 4 doses (months 4, 7, 10, 13).

Additional cGVHD treatment will include:

- **Sirolimus** (target level 4-10 ng/mL) – patients currently receiving a calcineurin inhibitor (tacrolimus or cyclosporine) and/or mycophenolate mofetil for GVHD prophylaxis will be converted to sirolimus per institutional guidelines. In the case of contraindication or intolerance to sirolimus, another systemic immunosuppressive (IS) drug (i.e. tacrolimus or cyclosporine) may be substituted at the discretion of the treating investigator.
- Short-course corticosteroids may be used, if necessary, for more rapid symptom control (≤1mg/kg Medrol, with planned taper to be completed no longer than 4 weeks).

When cGVHD manifestations have been quiescent for at least 4 weeks, sirolimus (or other IS medication) should be tapered over 4 weeks or per investigator discretion.

3.2. Study schema

4. SUBJECT SELECTION

4.1. Inclusion Criteria

Prior to enrollment, each potential subject must satisfy all of the following inclusion criteria:

1. First episode of systemic immunosuppression-requiring cGVHD, defined as classic or overlap cGVHD by the NIH consensus criteria.
2. Previously untreated cGVHD, defined by having received <10 days of corticosteroids or alternative systemic immunosuppressive agent started specifically for a new diagnosis of cGVHD
3. Age ≥ 18 years
4. Karnofsky performance status $\geq 70\%$
5. Patient willing and able to provide informed consent
6. Adequate hematologic function defined as:
 - Absolute neutrophil count (ANC) $\geq 1.0 \times 10^9/L$ and off growth factor support for 7 days.
 - Platelet count $\geq 30 \times 10^9/L$ and no platelet transfusions for 7 days.
7. Adequate hepatic function as defined by:
 - Total bilirubin of $\leq 1.5 \times$ ULN (unless of non-hepatic origin or due to Gilbert's Syndrome) or
 - Total bilirubin of $> 1.5 \times$ ULN to $3.0 \times$ ULN if due to cGVHD.
8. Women of childbearing potential and men who are sexually active with a woman of childbearing potential must be practicing a highly effective, preferably user-independent method of birth control (failure rate of $<1\%$ per year when used consistently and correctly)

during treatment and for up to 90 days after the last dose of ibrutinib, consistent with local regulations regarding the use of birth control methods for subject participating in clinical studies.

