4.2. Exclusion Criteria

To be enrolled in the study, potential subjects must meet NONE of the following exclusion criteria:

1. Patients with late persistent or recurrent acute GVHD
2. Active uncontrolled infection
3. History of HIV infection
4. Active HBV or HCV infection. Subjects who are positive for hepatitis B core antibody, hepatitis B surface antigen (HBsAg), or hepatitis C antibody must have a negative polymerase chain reaction (PCR) result before enrollment. Those who are PCR positive will be excluded.
5. Inability to tolerate oral medications.
6. Progressive or recurrent malignancy following allogeneic transplant
7. Known severe or life-threatening hypersensitivity to ibrutinib or rituximab
8. Creatinine > 2 mg/dl or calculated CrCl < 30ml/min
9. Requirement for anticoagulation therapy
10. Uncontrolled hypertension
11. Known bleeding disorder
12. Major surgery within 4 weeks of first dose of study drug
13. History of stroke or intracranial hemorrhage within 6 months prior to enrollment
14. Unable to swallow capsules
15. Subjects with chronic liver disease and hepatic impairment meeting Child-Pugh Class C (Appendix D).
16. Female subjects who are pregnant, or breastfeeding, or planning to become pregnant while enrolled in this study or within 90 days of last dose of study drug. Male subjects who plan to father a child while enrolled in this study or within 90 days after the last dose of study drug.
17. Unwilling or unable to participate in all required study evaluations and procedures
18. Unable to understand the purpose and risks of the study and to provide a signed and dated informed consent form (ICF) and authorization to use protected health information (in accordance with national and local subject privacy regulations)
19. Exposure to BTK inhibitor following transplant. Prior exposure to BTK inhibitor pre-transplant is allowed.
20. Vaccinated with live, attenuated vaccines within 4 weeks of first dose of study drug
21. Unresolved toxicities from prior anticancer therapy, defined as having not resolved to Common Terminology Criteria for Adverse Event (CTCAE, v5.0), Grade ≤ 1 , or to the levels dictated in the inclusion/exclusion criteria with the exception of alopecia

-
- 22. Any life-threatening illness, medical condition, or organ system dysfunction that, in the investigator's opinion, could compromise the subject's safety or put the study outcomes at undue risk

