11.4.4. Pregnancy

Before study enrollment, subjects must agree to take appropriate measures to avoid pregnancy. However, should a pregnancy occur in a female study subject, consent to provide follow-up information regarding the outcome of the pregnancy and the health of the infant until 30 days old will be requested.

A female subject or female partner of a male subject must immediately inform the investigator if she becomes pregnant from the time of consent to 90 days after the last dose of study drug(s). Any female subjects receiving study drug(s) who become pregnant must immediately discontinue study drug. The investigator should counsel the subject, discussing any risks of continuing the pregnancy and any possible effects on the fetus.

Although pregnancy itself is not regarded as an AE, the outcome will need to be documented. Any pregnancy occurring in a female subject or female partner of a male subject must be reported from the time of first dose up until 90 days after the last dose of study drug(s). Any occurrence of pregnancy must be recorded on the Pregnancy Report Form Part I and sent via email or fax to Pharmacyclics Drug Safety, Pharmacyclics Drug Safety, Pharmacovigilance & Epidemiology (DSP&E) or designee, per SAE reporting timelines of learning of the event. All pregnancies will be followed for outcome, which is defined as elective termination of the pregnancy, miscarriage, or delivery of the fetus. For pregnancies with an outcome of live birth, the newborn infant will be followed until 30 days old by completing the Pregnancy Report Form Part II. Any congenital anomaly/birth defect noted in the infant must be reported as a SAE.

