14. APPENDICES

Appendix A. Schedule of Assessments

Study Day	Screening (within 7 days)	Day 1	Day 7 (+/- 3 days)	Month 1 (+/- 7 days)	Month 2 (+/- 7 days)	Month 3 (+/- 7 days)	Month 6 (+/- 7 days)	Month 9 (+/- 7 days)	Month 12 (+/- 7 days)
Informed Consent	X								
Eligibility Confirmation	X								
Ibrutinib 420mg daily ¹		X		Continuous daily dosing Dispensed on D1 of each cycle through Cycle 12					
Rituximab 375mg/m ²			X ²					X ³	
Medical History	X			X	X	X	X	X	X
Physical Exam w/vitals	X			X	X	X	X	X	X
Schirmer's test	X			X	X	X	X	X	X
Karnofsky Performance Status	X								
Serum Pregnancy	X								
Hepatitis serologies	X								
Fasting Lipid Panel	X								
CBC w/differential	X	X	X	X	X	X	X	X	X
Comprehensive Metabolic Panel ⁴	X	X	X	X	X	X	X	X	X
IgG level	X					X	X	X	X
CRP	X			X	X	X	X	X	X
CK	X			X	X	X	X	X	X
LDH	X			X	X	X	X	X	X
Biomarkers (Correlative studies)	X			X	X	X	X	X	X
Concomitant Medications	X			X	X	X	X	X	X
GVHD assessment ⁵	X			X	X	X	X	X	X
GVHD patient self-report form ⁶	X			X	X	X	X	X	X
Pulmonary Function Test	X					X	X	X	X
Calculate cumulative steroid dose				X	X	X	X	X	X
Any new systemic IST				X	X	X	X	X	X
Any IVIG therapy				X	X	X	X	X	X
Adverse Event				X	X	X	X	X	X

¹Dose reduction required when using strong Cyp 3A4 inhibitors (e.g. voriconazole or posaconazole, see Section 6.2.1, table 4) or with hepatic impairment (see Section 5.1.1.5, table 3).

²Rituximab induction 375mg/m² Q7days x 4 doses.

³Rituximab maintenance 375mg/m² q 3months (+/-7days) x 4 doses.

⁴Glucose, BUN, creatinine, total bilirubin, alkaline phosphatase, albumin, SGOT (AST), SGPT (ALT), calcium, magnesium

⁵See appendix E

⁶See appendix F

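### Inclusion criterion 8 ties the post-treatment contraception period to ibrutinib alone, although rituximab is also a study medication and is planned to finish later

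*Combined protocol and SAP*

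**What the plan says.** **Contraception.** Inclusion 8 in section 4.1, repeated in the synopsis, requires highly effective birth control "during treatment and for up to 90 days after the last dose of ibrutinib". It applies to women of childbearing potential and to men sexually active with such women. Rituximab is not named.

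**Treatment schedule.** Section 5.1 lists ibrutinib (5.1.1) and rituximab (5.1.2) as study medications. Section 3.1 gives ibrutinib in 28-day cycles "for a total of 12 cycles unless discontinued early due to toxicity". After four weekly doses, rituximab maintenance is "IV q3months x 4 doses (months 4, 7, 10, 13"). Appendix A, footnote 3, adds a window: "q 3months (+/-7days) x 4 doses". Nothing in 5.1.2 sets a contraception period.

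**Pregnancy tracking.** Under section 11.4.4 the investigator must be told "if she becomes pregnant from the time of consent to 90 days after the last dose of study drug(s"), and a pregnancy "must be reported from the time of first dose up until 90 days after the last dose of study drug(s"). The optional plural takes in rituximab. The same section says that "subjects must agree to take appropriate measures to avoid pregnancy", without an end date.

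**Related exclusion.** Exclusion 16 in section 4.2 bars people who plan to conceive or father a child while enrolled or "within 90 days of last dose of study drug", in the singular.

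**The concern.** The two rules run on different clocks. Contraception after treatment is counted from the last ibrutinib dose, and pregnancy tracking from the last dose of whichever study drug ends later. As rituximab is scheduled to end later, a participant can meet inclusion 8 in full, stop contraception, and still be inside the interval in which the protocol wants every pregnancy reported.

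Contraception is also the protocol's main preventive control. Serum pregnancy testing is scheduled at screening only (section 8.1.1 and Appendix A), so no later test is planned that would pick up a lapse.

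The gap is widest if ibrutinib stops early and rituximab goes on. That path is foreseeable. Ibrutinib has its own stopping rules: the fourth toxicity occurrence in Table 1, and the first Grade 3 or 4 cardiac failure or Grade 4 arrhythmia in Table 3. None of them says that rituximab must stop too. Section 9.1 takes patients off study for new systemic immunosuppression, not for stopping ibrutinib. Section 9.2 permits withdrawal for life-threatening side effects but does not require it.

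**Working it through.** The plan states no figure to reproduce; the check is calendar arithmetic.

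**Inputs**
- *I*, last ibrutinib day. For a full course, 12 × 28 = 336 (section 3.1).
- *R*, last rituximab day, nominally month 13 (section 3.1), ±7 days (Appendix A). The protocol does not say whether a month is 28 days or a calendar month, so several readings are shown.
- Contraception tail: 90 days after *I* (inclusion 8).
- Pregnancy tracking: 90 days after the later of *R* and *I* (section 11.4.4).
- Assumption: treatment in inclusion 8 means both drugs, so contraception is required at least until *R*. This reading is favourable to the protocol.

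**Formula**

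Required contraception ends at max(*R*, *I* + 90). When *R* ≥ *I*, tracking ends at *R* + 90. Hence

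gap = *R* + 90 − max(*R*, *I* + 90) = min(90, *R* − *I*).

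If *R* < *I*, ibrutinib ends last and there is no gap.

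**Full course** (*I* = 336, contraception ends on day 336 + 90 = 426)

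| Reading of month 13 | *R* | Tracking ends (*R* + 90) | Gap (days) | Contraception left after *R* (426 − *R*) |
|---|---|---|---|---|
| 28-day months, first day | 337 | 427 | 1 | 89 |
| Last weekly dose (day 28) + 4 × 84 days | 364 | 454 | 28 | 62 |
| Calendar months, start of month 13 | 366 | 456 | 30 | 60 |
| Day 28 + 12 calendar months (365 days) | 393 | 483 | 57 | 33 |
| Calendar months, end of month 13 | 396 | 486 | 60 | 30 |

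With the ±7-day window, the first row becomes *R* = 330 to 344, so *R* − *I* runs from −6 to +8 days. The latest case tried starts rituximab on day 10, gives the fourth weekly dose on day 31, then adds 365 + 7 days: *R* = 403 and a gap of 403 − 336 = 67 days.

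For a full course, follow-up under section 9.1 is complete at about day 336 + 30 = 366. An infusion on day 396 would fall about 30 days after that point.

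**Early ibrutinib stop, rituximab continued to month 13**

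The gap reaches 90 days once *I* ≤ *R* − 90:
- *R* = 337: ibrutinib stopped by day 247
- *R* = 366: by day 276
- *R* = 396: by day 306

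In these cases no contraception is required after the last rituximab dose. If a site instead read treatment as ibrutinib only, the requirement would end at *I* + 90 and could lapse while infusions were still being given.

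**The case against.** The strongest reply is that this is a small drafting inconsistency.

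- **Cover is shortened, not absent.** For a full course, 30 to 89 days of required contraception remain after the last rituximab dose at the nominal dates above. This stands.
- **The planned gap may be negligible.** With 28-day months it is 1 day, and the dosing window can remove it. This stands too, but the protocol does not define the month and the other readings give 28 to 60 days.
- **The 90-day gap rests on an assumed path.** Rituximab continuing after ibrutinib stops is not prescribed. After an early stop, section 9.1 completion falls at 12 months, about day 365, so infusions on day 366 or 396 would be about 1 or 31 days past completion. That weakens those two cases but leaves *R* = 337 untouched.
- **A reporting window is not a contraception standard.** Surveillance may reasonably outlast prevention, and the documents hold no rituximab data that would fix the right length. This is fair. It limits what can be said about the correct duration, but it does not explain why one study medication has no stated period.
- **Other clauses help.** Exclusion 16 can be read to include rituximab, since section 11.3 speaks of any study drug. But section 5.1.1.2 uses the singular term for ibrutinib, so the wording is ambiguous, and the criterion addresses intent to conceive rather than contraception. The general duty in section 11.4.4 has no end date. Inclusion 8's reference to local regulations sets no rituximab period. The consent text is not available to check.

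None of this supplies the missing period.

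**Conclusion.** The concern holds. Inclusion 8 fixes the post-treatment contraception period by ibrutinib alone, nothing sets one for rituximab, and section 11.4.4 tracks pregnancies for 90 days after the later drug. Following the rule as written gives a shorter protected period than the protocol's own tracking interval.

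The omission is certain from the text; its size is not. At the nominal dates of a full course it is 1 to 60 days, depending on an undefined month, and dosing windows can close it or stretch it to about 67 days. It can reach 90 days only if ibrutinib stops early and rituximab is assumed to continue. The 90-day benchmark is the protocol's own figure, not evidence of the right interval for rituximab.

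The issue is patient safety for participants covered by inclusion 8. The primary endpoint, sample size and analyses are unaffected. It should be corrected because the correction is simple and cheap.

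**What to change.** In section 4.1 and the synopsis, require contraception during treatment and for at least 90 days after the last dose of ibrutinib or rituximab, whichever is later. The sponsor may set a longer period. Moving from *up to* to *at least* is deliberate: the present wording reads as a ceiling, where a minimum is needed.

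Name both drugs in the same way in exclusion 16 and section 11.4.4, so that the eligibility, contraception and reporting periods end together. If the consent form repeats inclusion 8, change it to match.

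The cost is one sentence in two places plus matching drug wording. No visits, patients or analyses are added. For a full course at the nominal dates, required contraception would end between day 427 and day 486 instead of day 426, so some participants would use it for 1 to 60 days longer. After an early ibrutinib stop, the extension could reach 90 days.

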4.2. Exclusion Criteria

To be enrolled in the study, potential subjects must meet NONE of the following exclusion criteria:

1. Patients with late persistent or recurrent acute GVHD
2. Active uncontrolled infection
3. History of HIV infection
4. Active HBV or HCV infection. Subjects who are positive for hepatitis B core antibody, hepatitis B surface antigen (HBsAg), or hepatitis C antibody must have a negative polymerase chain reaction (PCR) result before enrollment. Those who are PCR positive will be excluded.
5. Inability to tolerate oral medications.
6. Progressive or recurrent malignancy following allogeneic transplant
7. Known severe or life-threatening hypersensitivity to ibrutinib or rituximab
8. Creatinine > 2 mg/dl or calculated CrCl < 30ml/min
9. Requirement for anticoagulation therapy
10. Uncontrolled hypertension
11. Known bleeding disorder
12. Major surgery within 4 weeks of first dose of study drug
13. History of stroke or intracranial hemorrhage within 6 months prior to enrollment
14. Unable to swallow capsules
15. Subjects with chronic liver disease and hepatic impairment meeting Child-Pugh Class C (Appendix D).
16. Female subjects who are pregnant, or breastfeeding, or planning to become pregnant while enrolled in this study or within 90 days of last dose of study drug. Male subjects who plan to father a child while enrolled in this study or within 90 days after the last dose of study drug.
17. Unwilling or unable to participate in all required study evaluations and procedures
18. Unable to understand the purpose and risks of the study and to provide a signed and dated informed consent form (ICF) and authorization to use protected health information (in accordance with national and local subject privacy regulations)
19. Exposure to BTK inhibitor following transplant. Prior exposure to BTK inhibitor pre-transplant is allowed.
20. Vaccinated with live, attenuated vaccines within 4 weeks of first dose of study drug
21. Unresolved toxicities from prior anticancer therapy, defined as having not resolved to Common Terminology Criteria for Adverse Event (CTCAE, v5.0), Grade ≤ 1 , or to the levels dictated in the inclusion/exclusion criteria with the exception of alopecia

-
- 22. Any life-threatening illness, medical condition, or organ system dysfunction that, in the investigator's opinion, could compromise the subject's safety or put the study outcomes at undue risk
 - 23. Currently active, clinically significant cardiovascular disease, such as uncontrolled arrhythmia or Class 3 or 4 congestive heart failure as defined by the New York Heart Association Functional Classification; or a history of myocardial infarction, unstable angina, or acute coronary syndrome within 6 months prior to randomization
 - 24. Subjects who received a strong cytochrome P450 (CYP) 3A inhibitor within 7 days prior to the first dose of ibrutinib or subject who requires continuous treatment with a strong CYP3A inhibitor (Appendix C), with the exception of voriconazole or posaconazole which are permitted on study with appropriate dose modification.
 - 25. Subjects who have received prior treatment with extracorporeal photopheresis (ECP) for cGVHD.

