5.1.1.2. Dose and Administration

Ibrutinib 420 mg (3 x 140-mg capsules) is administered orally once daily. It is expected that many subjects commencing therapy for cGVHD will require anti-fungal prophylaxis. Please see Section 6.2.1 for dose modification guidelines with concomitant use of CYP3A inhibitors.

The capsules are to be taken around the same time each day with 8 ounces (approximately 240 mL) of water. The capsules should be swallowed intact and subjects should not attempt to open capsules or dissolve them in water. The use of strong CYP3A inhibitors/inducers (other

than those specifically permitted on study), and grapefruit and Seville oranges should be avoided for the duration of the study ([Appendix C](#)).

If a dose is not taken at the scheduled time, it can be taken as soon as possible on the same day with a return to the normal schedule the following day. The subject should not take extra capsules to make up the missed dose.

The first dose will be delivered in the clinic on Day 1, after which subsequent dosing is typically on an outpatient basis. Ibrutinib will be dispensed to subjects in bottles at each visit. Study drug may not be shipped to the subject without approval from PCYC and may not be dispensed to anyone other than the subject. Unused ibrutinib dispensed during previous visits must be returned to the site and drug accountability records ([Section 12.5](#)) updated at each visit. Returned capsules must not be redispensed to anyone.

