5.1.1.4. Dose Modification for Non-Cardiac Adverse Reactions

The dose of study drug must be modified according to the dose modification guidance in [Table 1](#) and [Table 2](#) if any of the following non-cardiac toxicities occur:

- Grade 4 neutropenia (ANC <500/ μ L) for more than 7 days. See [Section 6.1](#) for instructions regarding the use of growth factor support.
- Grade 3 thrombocytopenia (platelets <50,000/ μ L) in the presence of clinically significant bleeding events.
- Grade 4 thrombocytopenia (platelets <25,000/ μ L).
- Grade 3 or 4 nausea, vomiting, or diarrhea if persistent, despite optimal anti-emetic and/or anti-diarrheal therapy.
- Any other Grade 4 or unmanageable Grade 3 non-cardiac toxicity

Adverse events that are considered related to concomitant high dose corticosteroids (e.g. hyperglycemia, insomnia) do not require dose modification or holding of ibrutinib.

If the dose of ibrutinib is reduced, at the investigator's discretion, the dose of ibrutinib may be re-escalated after 4 weeks of a dose reduction in the absence of a recurrence of the toxicity that led to the reduction. Dose changes must be recorded in the CRF.

Table 1. Ibrutinib Dose Modifications

Occurrence	Action to be Taken
First	Withhold study drug until recovery to Grade ≤ 1 or baseline; may restart at original dose level
Second	Withhold study drug until recovery to Grade ≤ 1 or baseline; may restart at 1 dose level lower (i.e., 280 mg/day for 420 mg/day dose)
Third	Withhold study drug until recovery to Grade ≤ 1 or baseline; may restart at 1 dose level lower (i.e., 140 mg/day for 420 mg/day dose; 280 mg/day)
Fourth	Discontinue study drug

Table 2. Ibrutinib Dose Reduction Levels

Starting Dose Level	140 mg	280 mg	420 mg
Dose Reduction Level 1	70 mg	140 mg	280 mg
Dose Reduction Level 2	Discontinue	70 mg	140 mg
Dose Reduction Level 3	NA	Discontinue	Discontinue

For required dose modification for hepatic impairment refer to [Section 5.1.1.5](#) and for concomitant treatment with CYP3A inhibitors refer to [Section 5.1.1.6](#).

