5.1.1.7. Dose Modification for Concomitant Use of CYP3A Inhibitors

Dose adjustment of ibrutinib secondary to concomitant use of CYP 3A4 inhibitors should follow Table 4. Concomitant use of strong CYP inhibitors is not permitted in subjects with chronic hepatic impairment.

Table 5. Dose Modification Guidance for CYP3A4 Inhibitors

Co-administered Drug	Recommended Ibrutinib Dose for the Duration of the Inhibitor Use
Mild CYP3A4 inhibitors	420 mg once daily. No dose adjustment required.
Moderate CYP3A4 inhibitors	420 mg once daily. No dose adjustment required.
Voriconazole Posaconazole at doses less than or equal to suspension 200 mg BID or delayed-release tablet 300mg QD	280 mg once daily.
Posaconazole at higher doses	140 mg once daily.
Other strong CYP3A4 inhibitors	Avoid concomitant use. If these inhibitors will be used short term (such as anti-infectives for seven days or less), interrupt IMBRUVICA.

After discontinuation of a CYP3A4 inhibitor, resume previous dose of ibrutinib.

If Bili $>$ 1.5 x ULN, avoid and/or discontinue voriconazole, posaconazole, or other strong CYP3A4 inhibitor.

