Appendix C. Inhibitors and Inducers of CYP3A

Inhibitors and inducers of CYP3A enzymes are defined as follows. Refer to [Section 6.2.1](#) on instructions for concomitant use of CYP3A inhibitors and inducers with ibrutinib. Further information can be found at the following website: <http://medicine.iupui.edu/clinpharm/ddis/main-table/>.

Inhibitors of CYP3A	Inducers of CYP3A
Strong inhibitors:	
boceprevir	carbamazepine
clarithromycin	barbiturates
cobicistat	efavirenz
indinavir	glucocorticoids
itraconazole	modafinil
ketoconazole	nevirapine
mibefradil	oxcarbazepine
nefazodone	phenobarbital
nelfinavir	phenytoin
posaconazole ^a	pioglitazone
ritonavir	rifabutin
saquinavir	rifampin
suboxone	St. John's Wort
telaprevir	troglitazone
telithromycin	
troleanomycin	
Moderate inhibitors:	
amiodarone	
amprenavir	
aprepitant	
atazanavir	
ciprofloxacin	
crizotinib	
darunavir	
diltiazem	
dronedarone	
erythromycin	
fluconazole	
fosamprenavir	
grapefruit juice	
imatinib	
Seville orange juice	
verapamil	
voriconazole ^a	
Weak inhibitors:	
cimetidine	
fluvoxamine	
All other inhibitors:	
chloramphenicol	
delavirdine	
diethyl-dithiocarbamate	
gestodene	
mifepristone	
norfloxacin	
norfluoxetine	
star fruit	

^a Classification based on internal data.

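### Voriconazole is a moderate CYP3A inhibitor in Appendix C but strong elsewhere in the protocol; its class, the misdirected dosing cross-references and the rule for resuming ibrutinib after an inhibitor need reconciling

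*Combined protocol and SAP*

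**What the plan says.** All references are to the combined protocol and SAP.

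- **Setting.** Section 5.1.1.2: "It is expected that many subjects commencing therapy for cGVHD will require anti-fungal prophylaxis".
- **Voriconazole as strong.** Exclusion 24 (section 4.2) applies to a "strong CYP3A inhibitor (Appendix C), with the exception of voriconazole or posaconazole which are permitted on study with appropriate dose modification"; the exception is needed only if voriconazole is strong. Section 3.1: "Dose adjustments are required for patients with hepatic impairment or those receiving concomitant voriconazole or posaconazole or other strong CyP 3A4 inhibitor". The last line of section 5.1.1.7 says that above 1.5 x ULN bilirubin one should "avoid and/or discontinue voriconazole, posaconazole, or other strong CYP3A4 inhibitor". Appendix A footnote 1 gives voriconazole as an example of a strong inhibitor needing a dose reduction.
- **Voriconazole as moderate.** Appendix C, cited by exclusion 24 for the class and by section 6.2.1 as the reference list, places it under "Moderate inhibitors".
- **Dose.** In Table 5 (section 5.1.1.7) the moderate-class row reads "420 mg once daily. No dose adjustment required". A separate row names voriconazole, at 280 mg once daily.
- **Hepatic rule.** Section 5.1.1.7 does not permit strong inhibitors in chronic hepatic impairment.
- **Stopping the inhibitor.** Section 5.1.1.7: "After discontinuation of a CYP3A4 inhibitor, resume previous dose of ibrutinib". After a toxicity reduction, section 5.1.1.4 says that the dose, at the investigator's discretion, "may be re-escalated after 4 weeks of a dose reduction in the absence of a recurrence of the toxicity".

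**The concern.** Section 6.2.1 itself warns that strong or moderate inhibition can raise ibrutinib exposure. Instructions for a permitted interacting drug should therefore lead every prescriber to the same action. Here the class of one permitted azole depends on the page consulted, and the pointers to the dosing table are out of date. When an inhibitor adjustment and a toxicity reduction coincide, no text says which rule governs. Patient safety is at stake first. Ibrutinib exposure also bears on the incidence of related grade 3 or higher adverse events, the safety endpoint in section 10.2.2.

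**Working it through.** This is a reading of text and tables; the only arithmetic is on doses and Child-Pugh points.

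**1. Class of voriconazole**

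| Place | Class given or implied |
|---|---|
| Section 3.1 | strong |
| Exclusion 24 | strong |
| Section 5.1.1.7, last line | strong |
| Appendix A, footnote 1 | strong |
| Appendix C | moderate |

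The Appendix C entry does not look like a text-extraction fault: voriconazole follows verapamil in an alphabetical moderate list, and posaconazole is in the strong list.

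**2. Dose**

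- By drug name: named row of Table 5, 280 mg.
- By class: Appendix C moderate, then the moderate row of Table 5, 420 mg.
- Difference: 420 - 280 = 140 mg/day; 420/280 = 1.5.

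The second route requires passing over the row that names the drug. No text assigns 420 mg to voriconazole by name.

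**3. A rule that depends on class alone**

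Exclusion 15 removes only Child-Pugh class C. Take a patient with bilirubin in the lowest Appendix D band and not above 1.5 x ULN (1 point), albumin below 28 g/L (3), INR below 1.7 (1), mild ascites (2) and no encephalopathy (1). The total is 1 + 3 + 1 + 2 + 1 = 8, class B. If that patient counts as having chronic hepatic impairment, voriconazole is barred when read as strong and not barred by that sentence when read as moderate. The bilirubin line, which names voriconazole, does not apply to this patient, and Table 5 does not settle the question.

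**4. Where the pointers lead**

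In the current numbering, section 5.1.1.5 and Table 3 cover cardiac toxicity, 5.1.1.6 and Table 4 hepatic impairment, and 5.1.1.7 and Table 5 CYP3A4 inhibitors.

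- Section 5.1.1.2 sends the reader to 6.2.1, which sends the reader to Table 4 in 5.1.1.6.
- Section 5.1.1.7 itself says Table 4, directly above Table 5.
- Appendix A footnote 1 says Table 4 for inhibitors, and 5.1.1.5 and Table 3 for hepatic impairment.
- Sections 3.1 and 5.1.1.4 cite 5.1.1.5 (hepatic) and 5.1.1.6 (inhibitors).
- Section 5.1.1.6 cites Table 3 for its own hepatic table.

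Each is one number behind. A reader who follows 6.2.1 reaches a table with no inhibitor rows; for bilirubin at or below 1.5 x ULN at baseline and on study, that table continues 420 mg.

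**5. Resuming the previous dose**

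Assume ibrutinib at 420 mg, voriconazole added later (280 mg by the named row), and the 280 mg column of Table 2 applied from then on.

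- Table 1: the first qualifying non-cardiac toxicity may restart at the same level; the second restarts one level lower, which is 140 mg in that column.
- Voriconazole stops. If the previous dose means the pre-inhibitor dose, ibrutinib returns to 420 mg; 420/140 = 3.
- Section 5.1.1.4 makes re-escalation discretionary, and only after 4 weeks without recurrence.

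Under Table 3 a single first grade 3 arrhythmia takes a patient from the 280 mg column to 140 mg, and section 5.1.1.5 gives no re-escalation rule. The sentence in 5.1.1.6 that takes the lower of two reductions covers a non-hepatic toxicity combined with raised bilirubin, not an inhibitor adjustment combined with toxicity.

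**The case against.** The strongest reply is that Table 5 already answers the practical question. It names voriconazole apart from the moderate class, and section 3.1, exclusion 24 and Appendix A all require a dose modification. Section 6.2.1 calls Appendix C only a list of common agents, and Appendix C refers back to 6.2.1 for instructions. This stands for the dose. A reader might infer that the plan prescribes two doses for the same patient, but the documents do not support that: 420 mg is a possible misreading, not a second stated dose.

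Three other inferences also fail. Different sites would not dose differently, because the synopsis gives one centre; any variation would be between prescribers or over time. Eligibility does not change, because voriconazole is admissible under exclusion 24 either as the named exception or because a moderate inhibitor is outside it. The plan also does not say that voriconazole use is common. It expects anti-fungal prophylaxis in many patients, and Appendix C lists other azoles, including fluconazole (moderate) and posaconazole (strong), without this conflict.

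On resumption, the sentence can fairly be read as undoing only the inhibitor adjustment, and the non-cardiac example needs two qualifying toxicities before the inhibitor stops. The conflict is therefore one of literal reading. That narrows it but does not remove it, since no text states the limited meaning. The named row also answers neither the class-based hepatic rule nor the misdirected references.

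**Conclusion.** The point holds as an internal inconsistency that should be corrected. One appendix contradicts four other places on the class of voriconazole. The consequence shown is in the hepatic-impairment rule and the risk of a misread lookup (140 mg/day, 1.5-fold), not in two prescribed doses. The cross-reference error is plain and affects sections 3.1, 5.1.1.4, 5.1.1.6, 5.1.1.7, 6.2.1 and Appendix A. The resumption sentence leaves a gap worth up to a 3-fold step in the example, conditional on the literal reading and on the assumed order of treatment.

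The hepatic example further assumes that class A or B disease counts as chronic hepatic impairment, which the plan does not define. The number affected is unknown and could lie anywhere from none to all 35 planned patients. No size can be put on any effect on the grade 3 or higher endpoint, and the sample-size calculation is untouched.

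**What to change.** 1. Reconcile the class of voriconazole across section 3.1, exclusion 24, section 5.1.1.7, Appendix A footnote 1 and Appendix C, so that class and Table 5 row agree and the hepatic-impairment sentence has one meaning.
2. Correct the table and section references in sections 3.1, 5.1.1.4, 5.1.1.6, 5.1.1.7, 6.2.1 and Appendix A footnote 1 to the current numbering.
3. Reconcile the resumption sentence in 5.1.1.7 with the toxicity rules in 5.1.1.4 and 5.1.1.5, stating what the previous dose means and which rule governs when an inhibitor adjustment and a toxicity reduction coincide.

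The sponsor decides the class, the doses and the governing rule; none is proposed here. The cost is a wording amendment, with no added procedures, visits or patients.
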